10.0 Vulnerable Populations

10.1 Vulnerable Populations:

Population / Group	Identify whether any of the following populations will be primary focus of the research (targeted), included but not the focus of the research or excluded from participation in the study.
Children	Excluded
Pregnant women/fetuses/neonates	included but not the focus
Prisoners	Excluded
Adults lacking capacity to consent and/or adults with diminished capacity to consent, including, but not limited to, those with acute medical conditions, psychiatric disorders, neurologic disorders, developmental disorders, and behavioral disorders	Primary focus of the research
Non-English speakers	Excluded
Those unable to read (illiterate)	Excluded
Employees of the researcher	Excluded
Students of the researcher	Excluded
Undervalued or disenfranchised social group	included but not the focus

Active members of the military (service members), DoD personnel (including civilian employees)	included but not the focus
Individual or group that is approached for participation in research during a stressful situation such as emergency room setting, childbirth (labor), etc.	Excluded
Individual or group that is disadvantaged in the distribution of social goods and services such as income, housing, or healthcare.	included but not the focus
Individual or group with a serious health condition for which there are no satisfactory standard treatments.	included but not the focus
Individual or group with a fear of negative consequences for not participating in the research (e.g. institutionalization, deportation, disclosure of stigmatizing behavior).	Excluded
Any other circumstance/dynamic that could increase vulnerability to coercion or exploitation that might influence consent to research or decision to continue in research.	Excluded

10.2 Additional Safeguards:

All participants in the above table that are listed as “included but not the focus” could be included in the study by chance. However, these vulnerable groups are not sought out during recruitment and we do not ask potential participants if they belong to one of the above groups or not. Thus, extra safeguards are not put in place to protect these groups since we would not know if they were included in the research or not. Given our study population of interest, it is unlikely for participants to be a part of the groups listed as “included but not the focus,”

besides adults lacking the capacity to consent or have a diminished capacity to consent which is addressed below.

Adults lacking the capacity to consent or have a diminished capacity to consent are one of the primary groups of participants to be recruited to the study. Specific safeguards to protect this population include signing of a consent form by the caregiver or a LAR (Legally Authorized Representative). Additionally, the person with memory loss either consents or assents to the research based on their SLUM and Capacity to Consent scores – see more detail in the consent section below.

10.3 If research includes potential for direct benefit to participant, provide rationale for any exclusions indicated in the table above:

Some individuals in the above vulnerable groups are excluded because they are not our population of interest (i.e. ADRD does not impact children) or because participating in such research would potentially be risky for them.

11.0 Number of Participants

11.1 Number of Participants to be Consented:

We aim to enroll 200 ADRD caregivers and 200 individuals with ADRD in our study.

12.0 Recruitment Methods

12.1 Recruitment Process:

The Principal Investigator (PI) will initiate email, telephone, or mail contact with ADRD caregivers on the University of Minnesota Caregiver Registry (IRB# 1007S85812) or others recruited by the PI or research coordinators via various advertisements, community presentations, and other outreach/enrollment efforts who potentially meet the project inclusion criteria. In addition, the PI or research coordinators will ask professional caregivers on the Registry to identify potential ADRD caregivers for recruitment purposes.

12.2 Source of Participants:

[name] has created a University of Minnesota Caregiver Registry that includes family and professional caregivers who have participated in his free annual community education conference, "Caring for a Person with Memory Loss" (CPWML). Approximately 200-350 persons attend each CPWML conference. Attendees are invited to complete a brief form which enrolls them in the Registry and gives [name] and his research staff permission to contact and invite them to participate in his studies. We will periodically send project recruitment materials to members of the caregiver registry.

In addition to general recruitment assistance, the PI or research coordinators will ask professional care providers in the Registry (many of whom provide care to under-represented older persons)

PROTOCOL TITLE: A Proactive Health Monitoring Intervention for Dementia Caregivers: The eNeighbor

to identify ADRD caregivers of diverse ethnic or racial origin and geographic location to enhance the inclusion of AHRQ Priority Populations. These recruitment efforts will be facilitated by the Minnesota Board on Aging (MBA), the Minnesota-North Dakota Alzheimer's Association regional office, and other community organizations. For example, the MBA will help us promote this study through Area Agencies on Aging, many of which serve ethnic and racially diverse older adults as well rural ADRD caregivers. Cumulatively, these various outreach efforts are expected to result in a sample that includes approximately 40 diverse and under-represented ADRD caregivers (20% of the sample). Additional recruitment efforts will take place via advertisements in local print, radio, and internet media sources including websites of local and national organizations.

12.3 Identification of Potential Participants:

Family and professional caregivers on The University of Minnesota Caregiver Registry (IRB# 1007S85812) have provided permission for [name] or his research team to contact them to invite them to participate in his ongoing or future research projects. Other enrollment procedures will rely on participants to contact [name] or the research coordinators if they are interested; this will also protect participants' privacy.

During initial enrollment contacts, the PI or research coordinators will describe the eNeighbor monitoring system, explain study procedures, and invite potential ADRD caregivers to participate. Caregivers will be offered the opportunity to ask any questions about the study procedures. If caregivers agree to participate, the PI or research coordinators will initiate a brief screening procedure applying the inclusion criteria above. Participants will self-identify in response to recruitment efforts.

The PI and research coordinators will be in first contact with potential participants. Additionally, professional care providers in the Registry may promote this study and therefore be the first contact with potential participants. Potential participants will not be identified using medical records or other source of protected records.

12.4 Recruitment Materials: See materials submitted in ETHOS.

12.5 Payment: Participants are not compensated for participating in the study.

13 Withdrawal of Participants

13.1 Withdrawal Circumstances:

We will emphasize to all participants that they do not have to complete any question they do not want to answer, and that the interview may be terminated at any time according to their wishes. We will stress to ADRD caregivers that their decision to discontinue the study will in no way affect the services they are receiving from the University of Minnesota or other entities. If a participant wishes to withdraw from the study because they are no longer interested in participating or they are no longer able to participate, we will follow the procedures described below.

13.2 Withdrawal Procedures:

In instances where ADRD caregivers wish to withdraw from the study we will determine and document the reason for study withdrawal, and if the caregiver agrees we will administer regular, brief surveys (either online or over the telephone) to collect data on outcome variables (identical to the regular follow-up interviews/surveys).

13.3 Termination Procedures:

In instances where ADRD caregivers are terminated from the study, we will determine and document the reason for termination and ask the caregiver to return the eNeighbor system (if applicable). We would not send the caregiver any follow-up surveys/interviews.

14 Risks to Participants**14.1 Foreseeable Risks:**

The consideration of need is potentially stressful, and thus there are possible psychological risks for the caregiver a relative with Alzheimer's disease and related dementia (ADRD). Since the research team has considerable experience providing psychosocial support to dementia caregivers on various research protocols, serious psychological risks are unlikely to occur. The potential social or legal risks for the participants relate only to possible violations of confidentiality. As noted above, HealthSense, Inc. has instituted a robust and secure data privacy system for the remote health monitoring technology.

14.2 Reproduction Risks: Not applicable**14.3 Risks to Others: Not applicable****15 Incomplete Disclosure or Deception****15.1 Incomplete Disclosure or Deception: Not applicable****16 Potential Benefits to Participants****16.1.1 Potential Benefits: There are no direct benefits of participating in the study.****17 Statistical Considerations****17.1 Data Analysis Plan:**

Intensive longitudinal analysis procedures (growth curve modeling) will be utilized to capitalize on the randomized design and the multiple waves of data that will be collected.

17.2 Power Analysis:

The number of ADRD caregivers to be enrolled to address study hypotheses was determined using power analysis procedures that take into account the hierarchical

analytic design of the study.⁶⁸ In this framework, the researcher identifies the Type I error rate (e.g., $p < .05$) to differentiate between a null and alternative test hypothesis, a suitable level of statistical power (.80 is considered an excellent power value), and the expected difference between the two study groups in order to determine the number of ADRD caregivers to enroll into the project. We sought a sample size that would be sufficient to detect a group difference of 0.50 standard deviation units. This is considered to be a “medium” effect size⁶⁹ and is a reasonable benchmark to evaluate the efficacy of a new behavioral intervention in comparison to an attention control condition. Using these specifications, a sample size of 200 ADRD caregivers (factoring in the anticipated 20% attrition rate) was found sufficient. As noted in various recommendations for mixed methods sampling, 30 participants is considered an adequate sample size for semi-structured interview protocols to ensure the richness and depth of open-ended data collected.^{70,71}

17.3 Statistical Analysis:

Analysis of Specific Aim1: Tests of Hypotheses 1-3.

Data available at baseline, 6 months, 12 months, and 18 months will allow for individual growth curve models that examine change in ADRD caregiver outcomes.^{72,73} Multilevel analysis approaches are available that support growth curve modeling. In this context, growth curve modeling is an example of a 2-stage modeling process consisting of 1) a within-subjects model across time; and 2) a between-subjects model that incorporates caregiver and person with ADRD covariates.^{74,75} The primary independent variable in the proposed investigation consists of an indicator variable for random assignment into the eNeighbor treatment condition or the attention care control. IBM SPSS Statistics 21⁷⁶ will be used to conduct these analyses, as it supports multilevel and growth curve modeling procedures. [name], the PI, has extensive experience conducting longitudinal and growth curve analyses in his prior research on ADRD caregiving.^{46,80,81,88}

Our proposed analyses will provide in-depth tests of Hypotheses 1 and 2 and partially test Hypothesis 3 (i.e., rates of change in ADRD caregivers’ self-efficacy, competence, subjective stress, depressive symptoms, and frequency of negative health transitions and service use). In one set of outcome evaluations, the baseline value will be included as a covariate, and time will be “centered” at 6-months post-baseline. This scales the intercept effect to be a main effect of eNeighbor group assignment and allows the eNeighbor treatment and the attention control groups to have different 6-, 12-, and 18-month change trajectories, or an expanded eNeighbor treatment*time interaction effect. After establishing that the individual growth parameter estimates have significant variance around the mean trajectories of change in key dependent variables, an eNeighbor treatment vs. attention care control group indicator will be added as the key independent variable to predict intercepts and rates of change in outcomes. Additional analyses will determine if covariates (e.g., stress process model covariates including context of care indicators, primary objective stressors, and resources) significantly vary across the eNeighbor treatment and attention control groups at baseline and over time via growth curve modeling procedures. If statistically significant variations between the eNeighbor treatment and

PROTOCOL TITLE: A Proactive Health Monitoring Intervention for Dementia Caregivers: The eNeighbor

control groups are found, initial status and rate of change parameters for these covariates will be included in all tests to provide additional statistical control.

Cox proportional hazard survival analyses will determine whether participation in the eNeighbor treatment group results in significantly less time to nursing home admission (e.g., admission into a 24-hour nursing home facility for at least 90 days), overnight hospitalization, emergency room use, and negative health transitions (falls, wandering) when compared to persons with ADRD in the attention control group (Specific Aim 1/Hypothesis 3). The Cox proportional hazards model is defined as the product of an unknown function of time and the exponent of a linear combination of risk variables. eNeighbor treatment vs. attention control group membership will be the independent variable of interest in the test of Hypothesis 3; time to nursing home admission, overnight hospitalization, emergency room use, and occurrence of a fall or a wandering event will serve as the dependent variables. Date of randomization will serve as baseline. Additional variables will serve as covariates, including time-invariant and time-varying measurements of stress process covariates. Likelihood ratio tests and partial odds ratios will be examined in order to determine the degree to which these variables explain the observed effects of eNeighbor on time to dependent variable occurrence.

Variations in eNeighbor Use and Setting

Empirical treatment fidelity data and context of care measures that assess heterogeneity in the use of eNeighbor within the treatment condition (e.g., frequency and duration of sensor alerts and myHealthsense website use; diverse home characteristics) will be included as a series of additional Specific Aim 1 analyses. These analyses will explore the effects of variations in eNeighbor use on the outcomes hypothesized above for persons with ADRD and their family caregivers.

Specific Aim 1/Hypothesis 4

The cost-effectiveness of the remote monitoring technology intervention will be assessed by comparing costs of implementation and healthcare utilization between persons with ADRD in the treatment condition and those in the attention control. The analysis will be conducted from the perspective of the payer (i.e., the public). Costs in the numerator of the incremental cost-effectiveness ratio (ICER) will be determined by identifying the differences in Medicare and Medicaid expenditures for persons with ADRD across the eNeighbor treatment and attention control groups using aggregated (“rolled up”) Medicare and Medicaid claims matched to the individual participant by Social Security number for the 18 months of participation. Because the differences in costs derive from a randomized trial, an evaluation of the difference in mean costs can determine significance. In addition, the direct costs of the intervention will be included as the cost of the remote sensor hardware, staff time (i.e., the Director of Nursing and Technology, who will track her hourly effort related to monitoring eNeighbor activities and assisting ADRD caregivers over a 1.5-year period), and installation costs over the 18-month study period.

The differences in effectiveness included in the denominator of the ICER will be measured using 5 ADRD caregiver and person with ADRD outcome measures: a) the standard cut-point of

“moderate or higher” burden on the Zarit Burden Interview;⁷⁷ b) the standard cut-point of “major depression” on the Center for Epidemiological Studies Depression scale;⁷⁸ c) fall (occurred or not); d) wandering event (occurred or not); e) nursing home admission (placed or not); f) hospitalization (overnight use or not); and g) emergency room use (used or not). Significant differences in cost will be investigated. Sensitivity analysis will be performed where parameter uncertainty exists. Where possible, evaluation of these ICERs will be based on comparisons in prior literature to determine the overall costs and effectiveness of eNeighbor.

Analysis: Specific Aim 2

Specific Aim 2 analyses will primarily focus on thematic content analysis of open-ended data to examine eNeighbor utility and mechanisms of benefit. As noted by experienced methodologists, systematic reading and rereading of qualitative content and hand coding of a significant proportion of this content is necessary in order to develop an understanding of meanings in their conversational or observational contexts.^{79,80} Specifically, the PI and research coordinator with the help of [name] (Co-Investigator) will independently develop coding categories together with descriptors (via hand-coding and NVivo) and will generate a shared coding scheme that will reflect the primary categories of the transcription. Through repetition of this procedure, a consensus perspective on appropriate coding categories and themes will be modified and developed. These themes will provide insights as to the eNeighbor’s implementation and use (i.e., treatment fidelity/process evaluation embedded component) and mechanisms of benefit (i.e., semi-structured interview embedded component).

Grounded theory techniques described by Morse⁸¹ and Strauss and Corbin⁷⁹ will guide the analyses of qualitative data in Specific Aim 2. These approaches allow participants to construct meanings, perceptions, and behaviors from their own vantage points. All open-ended data collected will be first read by the PI and the research coordinator to identify textual elements that emerge repeatedly (i.e., codes); these codes will then be clustered into larger categories that are later used to construct major thematic elements from the text (with the use of NVivo 10 analytic software). During weekly meetings in the analysis phase of the proposed project, the PI and research coordinator along with [name] will discuss their own identified codes to reach a consensus about specific codes, categories, and themes that emerge from the qualitative data (these decisions will be noted in an audit trail). In addition, patterns that link particular themes will be identified and discussed in successive meetings between the PI, research coordinator, and [name] to identify more complex processes of eNeighbor use or health monitoring technology’s pathways to benefit for persons with ADRD and their family caregivers. During monthly team meetings, the development of codes, categories, and themes will be reviewed with the project Consultants to yield any additional input into these project components. The multiple team meetings and discussions will allow for an exploration of alternative interpretations of the qualitative data and will also provide a check regarding the quality and richness of the data collected during the embedded mixed methods components. Additional mixed methods analyses^{57,58} will take place. The thematic codes and categories of implementation/use and mechanisms of benefit will be cross-tabulated with the empirical data from the randomized controlled evaluation to determine whether the findings diverge, converge, or highlight pathways

PROTOCOL TITLE: A Proactive Health Monitoring Intervention for Dementia Caregivers: The eNeighbor

toward additional questions and analysis.⁵⁷ This comparative, mixed method analysis approach may suggest that those who reported greater decreases in subjective stress during health monitoring technology use may indicate certain themes more often than ADRD caregivers who report greater increases in stress.

Specific Aim 3 Analysis Plan

Brief background data will be collected from Community Advisory Board (CAB) members (sociodemographics, professional experience, duration of dementia care, etc.). Analyses of these descriptive quantitative data will include descriptive statistics such as frequency tables, means, and other univariate statistics. Additional strategies will include thematic content analysis of open-ended data (e.g., meeting discussions) as described above. Analysis of CAB meeting open-ended data will help us to identify the main themes related to how health monitoring technology can be designed, delivered, and evaluated to achieve the greatest utility for persons with ADRD and their family caregivers.

Planned Interim Analyses

Not applicable; if these are done, they will be conducted at the 6-, 12-, and 18-month intervals; given how the qualitative data component of the mixed methods research design is structured, these findings will not be fully available until the final months of the 5-year project.

17.4 Data Integrity:

Data will be anonymized approximately 3-5 years following the completion of this project. Specific data collection methods and types are described in detail earlier. The de-identified data will be kept indefinitely.

18 Health Information and Privacy Compliance

18.1 Select which of the following is applicable to your research:

- My research does not require access to individual health information and therefore assert HIPAA does not apply.
- I am requesting that all research participants sign a HIPCO approved HIPAA Disclosure Authorization to participate in the research (either the standalone form or the combined consent and HIPAA Authorization).
- I am requesting the IRB to approve a Waiver or an alteration of research participant authorization to participate in the research.

Appropriate Use for Research:

- An external IRB (e.g. Advarra) is reviewing and we are requesting use of the authorization language embedded in the template consent form in lieu of the U of M stand-alone HIPAA Authorization. Note: External IRB must be serving as the privacy board for this option.

18.2 Identify the source of Private Health Information you will be using for your research (Check all that apply)

I will use the Informatics Consulting Services (ICS) available through CTSI (also referred to as the University's Information Exchange (IE) or data shelter) to pull records for me

I will collect information directly from research participants.

I will use University services to access and retrieve records from the Bone Marrow Transplant (BMPT) database, also known as the HSCT (Hematopoietic Stem Cell Transplant) database.

I will pull records directly from EPIC.

I will retrieve record directly from axiUm / MiPACS

I will receive data from the Center for Medicare/Medicaid Services

I will receive a limited data set from another institution

Other. Describe:

18.3 Explain how you will ensure that only records of patients who have agreed to have their information used for research will be reviewed.

18.4 Approximate number of records required for review:
N/A; not reviewing records.

18.5 Please describe how you will communicate with research participants during the course of this research. Check all applicable boxes

This research involves record review only. There will be no communication with research participants.

Communication with research participants will take place in the course of treatment, through MyChart, or other similar forms of communication used with patients receiving treatment.

Communication with research participants will take place outside of treatment settings. If this box is selected, please describe the type of communication and how it will be received by participants. When participants consent or assent to participating in the research, they are asked whether or not they agree to communicate with the research team via unencrypted email. If a participant does not agree to communicate this way, the team can send encrypted emails to participants.

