In general, a call will be placed to every participant near the time when the survey is sent out. For participants who are a part of the control group, this call will serve as a time to check-in, and also make these participants feel connected to the research study. A monthly check-in call/attempt will be placed to those in the eNeighbor treatment group, as a means to confirm that the eNeighbor sensor system is functioning properly.

Furthermore, we will administer a verbal permission/modified assent procedure prior to or following each 6-month interview/survey (i.e., 6 months, and 12 months) for those in the eNeighbor treatment group (unless care recipient passed, moved to a care facility, had sensor system removed).

The rationale for this approach is that since persons with dementia in the control group do not engage in any way with the research procedures or researchers themselves following baseline (i.e., family caregivers complete all surveys), assent is likely not needed in such circumstances as participants in the control group are essentially participating in a family caregiving study. As persons with memory loss in the treatment condition are experiencing the installation and operation of the eNeighbor remote monitoring system in their homes, ongoing permission is necessary for these individuals for the duration of the study follow-up period (i.e., 6 months, and 12 months; note: by the 18-month follow-up surveys/interviews the study procedures are complete and no further assent is needed).

Specifically, verbal assent of persons with Alzheimer's disease or a related dementia (ADRD) (oral only) will take place for those in the eNeighbor treatment condition over the telephone (unless the family caregiver has requested an in-person interview). Family caregivers may also (and are encouraged to) join the telephone call via a conference connection, another land line, or speaker phone to help facilitate the assent process and effectively communicate with the person with memory loss if needed. If a dissenting behavior or agitation is exhibited by the person with memory loss, a conversation with the caregiver alone should take place, to determine if this behavior related to the eNeighbor system is common. If it is common, then the verbal dissent should be noted and the DNT should be contacted immediately to schedule removal of the sensor technology. This will also occur after any adverse/negative reaction to the eNeighbor remote monitoring system.

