We will take several steps to address attrition bias. If a person with ADRD has moved into a residential long-term care facility or has died, caregiver follow-up interviews will include queries determining when these events occurred. Regular follow-up will continue in order to collect as much information on outcome variables that are appropriate (i.e., intention to treat principle). Per the consent form, participants will have the opportunity to provide a Social Security Number for the care recipient to study staff (over the phone) during/at the end of the study. Participants may also choose to opt out of this. At the conclusion of the project, Thank You cards will be mailed to all participants to ensure rapport.

Treatment fidelity. Monthly system reviews will take place through system reports generated by the Director of Nursing and Technology. The MyHealthsense portal can also track how often the ADRD caregiver or others utilize the care coordination resources of MyHealthsense. The PI or research coordinator will also determine the degree to which participants apply the eNeighbor monitoring tool to their everyday care situations. An online or mail survey of close-ended, Likert-scale items to determine eNeighbor's acceptability by ADRD caregivers as well as multiple open-ended questions will be administered to all ADRD caregivers in the eNeighbor treatment condition at the 6-, 12-, and 18-month interview intervals. The open-ended responses will provide qualitative data as to the reasons why family caregivers felt the health monitoring technology of eNeighbor was or was not easy to utilize (e.g., "Why or how was the health monitoring technology easy or difficult to use?" The identification of these barriers or facilitators will be considered when examining ADRD caregivers' perceptions of eNeighbor's design, delivery, and ease of use.

Final Study Visit/Survey.

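### Section 13.3 ends outcome surveys for caregivers terminated from the study, so their later outcomes are missing by design, although 13.2 keeps following those who withdraw by choice

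*Combined protocol and SAP*

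**What the plan says.** Three places govern what happens to outcome collection when a dyad's participation changes.

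- **13.3 Termination Procedures.** "In instances where ADRD caregivers are terminated from the study, we will determine and document the reason for termination". The eNeighbor system is to be returned where there is one, and then: "We would not send the caregiver any follow-up surveys/interviews".
- **13.2 Withdrawal Procedures.** For caregivers who leave by choice, the reason is recorded and "if the caregiver agrees we will administer regular, brief surveys (either online or over the telephone) to collect data on outcome variables". The content is said to match the regular follow-up.
- **5.3 Follow-Up**, in the paragraph on attrition bias. "If a person with ADRD has moved into a residential long-term care facility or has died, caregiver follow-up interviews will include queries" about when this happened. The next sentence reads: "Regular follow-up will continue in order to collect as much information on outcome variables that are appropriate (i.e., intention to treat principle".

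On analysis, section 17.3 says: "Data available at baseline, 6 months, 12 months, and 18 months will allow for individual growth curve models". It adds: "In one set of outcome evaluations, the baseline value will be included as a covariate". The comparison variable is the random assignment. The plan defines no analysis set, no missing-data method and no censoring rule. Section 13.1 describes circumstances for withdrawal; no section gives grounds for termination, names who decides, or states how many terminations are expected.

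**The concern.** A caregiver who asks to leave may still be surveyed, while one whom the team removes may not, even if willing. No reason is given for the difference. Section 13.3 is a written instruction to stop collecting data on randomised people, in a protocol that elsewhere takes steps against attrition bias.

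Most endpoints depend on the caregiver's answers. Self-efficacy, competence, stress and depressive symptoms come from the surveys, and so do reports of falls, wandering, hospital use and placement. When surveys stop, all of these stop at last contact. The Social Security number needed for the claims analysis is optional and is requested during or at the end of the study, so a caregiver terminated early may never be asked.

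Section 5.2 has the investigator generate the randomisation list and tell caregivers their arm. A decision to terminate can therefore be made by someone who knows the allocation. With no written grounds, nothing prevents terminations from being related to outcome or unequal between arms.

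**Working it through.** **1. The rules side by side**

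| Event | Outcome surveys afterwards | Section |
|---|---|---|
| Caregiver withdraws by choice | Continue if the caregiver agrees | 13.2 |
| Person with ADRD is placed or dies | Continue, as appropriate | 5.3 |
| Caregiver is terminated | Stop, no exception | 13.3 |

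Only the third row ends collection regardless of the caregiver's willingness.

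**2. What is lost and what is kept**

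Waves collected before termination remain usable in the growth models of 17.3. In the models with baseline as covariate, only the 6-, 12- and 18-month values are outcomes, so a caregiver terminated before month 6 adds nothing to them. For time to event, survey-reported events are unobserved after last contact. Censoring there would be usual practice, but that is an inference, because the plan states no rule.

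**3. Is it a power problem?**

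Inputs from 17.2: difference 0.50 SD, alpha 0.05 (taken as two-sided; the plan does not say), power 0.80, 20% attrition, 200 caregivers. Allocation is 100 per arm (section 1.0). The plan cites a hierarchical power method without its parameters, so a simple two-sample comparison is used here.

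- n per arm = 2 × (1.960 + 0.842)² / 0.50² = 62.8, rounded up to 63; total 126.
- Allowing for attrition: 126 / 0.80 = 157.5, rounded up to 158.

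This does not reproduce 200. The plan says only that 200 is sufficient, and it is: with 80 completers per arm, 0.50 / √(2/80) − 1.960 = 1.20, which gives power 0.885. A further 10% loss in both arms leaves 70 per arm and power 0.841. Power falls below 0.80 only with fewer than 63 per arm, a total loss above 37%. Power is not the issue; bias is.

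**4. How large could the bias be?**

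The documents give neither the share terminated nor how those caregivers fare, so both are assumptions. Let t be the share of one arm terminated and k the deficit in SD of their outcomes against those retained. The full-arm mean is (1 − t) × m + t × (m − k) = m − t × k, where m is the retained mean. Leaving the terminated out entirely therefore overstates that arm by t × k.

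| t (assumed) | k (assumed) | t × k | Divided by 0.50 SD |
|---|---|---|---|
| 2% | 0.8 SD | 0.016 SD | 3.2% |
| 5% | 0.5 SD | 0.025 SD | 5% |
| 10% | 0.8 SD | 0.08 SD | 16% |

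For a given t and k this is an upper bound on loss of this kind. It treats the terminated as contributing no data at all, and it assumes no comparable loss in the control arm.

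**The case against.** The strongest reply is that four tempting inferences go further than the text.

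- **That 13.3 breaks an intention-to-treat promise.** The sentence in 5.3 follows directly on placement or death and is limited to outcomes that are appropriate. It does not mention termination. This stands: 13.3 is inconsistent with the principle invoked in 5.3, but it does not breach a commitment made about terminated caregivers.
- **That terminated caregivers are dropped from the comparison.** No section excludes them. The comparison is by random assignment and earlier waves are available to the models. This also stands, with the exception of terminations before month 6 in the baseline-as-covariate models.
- **That the loss falls on the treatment arm because sensors can be removed.** For dissent or a negative reaction, 5.3 says "the DNT should be contacted immediately to schedule removal of the sensor technology", but it does not say that the caregiver is then terminated or that surveys stop. Sections 5.3 and 22.7.1.2 list sensor removal beside death and placement only as a reason to skip the permission call. A caregiver who leaves because the system went badly would come under 13.2, where surveys continue by agreement. The rule in 13.3 covers both arms, since return of the system is required only where applicable.
- **That the bias favours eNeighbor.** With the grounds for termination unknown, the direction is conjecture. Comparable losses among controls would offset it, and earlier waves would reduce it to the extent that they predict later ones.

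One further caution is fair: some reasons for termination might make further contact inappropriate, so an unconditional duty to keep surveying would go too far.

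None of this explains why a willing caregiver should be surveyed after withdrawing but not after being terminated. That difference remains.

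**Conclusion.** The concern holds as an avoidable inconsistency in data collection. Section 13.3 makes the later outcomes of terminated caregivers missing by design, and no analysis set, missing-data method or censoring rule covers them. Because termination has no stated grounds and can be decided by staff who know the arm, the loss could be informative or unequal between arms; the documents do not show that it is either.

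The size and direction cannot be established. The range of 0.016 to 0.08 SD rests wholly on assumed shares and an assumed deficit, and should be read as showing that the effect is probably small unless terminations are common. Power is not threatened at any plausible extra loss. This is a cheap improvement and does not call the design into question.

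**What to change.** Replace the last sentence of 13.3 with the rule already in 13.2: terminated caregivers who agree, and for whom the reason for termination does not preclude contact, receive the same 6-, 12- and 18-month outcome surveys. State in 17.3 that they are analysed in the arm to which they were randomised. Report the number of terminations and the reasons by arm. Section 13.3 already requires the reason to be documented, so the reporting needs no new data. The consent wording should be checked to confirm that it permits the contact.

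The cost is a sentence or two of text, a few extra surveys and minor staff time. Outcomes that are not collected at the time cannot be recovered at analysis.
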